9.3.1.3 Analysis Methodology

[figure not shown]
General Summaries

Summaries will be provided for the following efficacy variables by each visit for which the variable is collected, in addition to the above endpoints:

- Proportion of subjects who:

- Meet SRI(4) response criteria
- Meet BICLA response criteria
- Meet LLDAS response criteria
- Have a CLASI activity score ≥ 10 at baseline who achieve a CLASI response, defined as a decrease of $\geq 50\%$ from baseline CLASI activity score
- Are receiving a daily CS dose ≤ 7.5 mg/day prednisone (or equivalent) in those receiving CS at baseline
- Change from baseline in:
 - BILAG-2004 score
 - SLEDAI-2K score
 - Joint counts for tender, swollen, and tender + swollen joints
 - Physician’s Global Assessment of Disease Activity

- CLASI activity score in subjects with a CLASI activity score ≥ 10 at baseline

Statistical Methodology

Efficacy analyses will be performed using the population of randomized subjects.

| Endpoint | Statistical Analysis Methods |
|----------|--|
| Primary | 
The primary endpoint, the proportion of subjects who meet the response criteria for SRI(4) at Week 32, will be analyzed using logistic regression with covariate for the randomization stratum to compare the response rates between each treatment group and placebo. The odds ratio (odds for active treatment /odds for placebo) and the corresponding 2-sided 95% confidence interval (CI) will be provided from the logistic regression model. Additionally, a sensitivity analysis will be conducted using a Cochran-Mantel-Haenszel (CMH) chi-square test stratified by randomization stratum; or alternatively a chi-square test if a CMH test cannot be performed. Differences in response rates and corresponding 2-sided 95% CI will be provided along with the point estimates and corresponding 95% CI for each group using a binomial model.
 
The above analyses will be conducted for the mITT population. The primary efficacy analysis will be performed after all subjects have completed Week 48 efficacy assessments (or discontinued).
 |

[figure not shown]

| Endpoint | Statistical Analysis Methods |
|----------------------|--|

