5.2 Randomization

Approximately 360 subjects are planned to be randomized via IRT in a 1:1:1:1 ratio to 1 of 4 treatments: BMS-986165 3 mg BID, 6 mg BID, and 12 mg QD, or placebo. Randomization is stratified by screening CS dose (≥ 10 mg/day or < 10 mg/day), screening SLE Disease Activity Index 2000 (SLEDAI-2K) score (≥ 10 or < 10), and region (North America, Latin America, Japan [other randomization factors will not be applied in Japan], and rest of world).

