6.5 Predetermined Covariates and Prognostic Factors

The following stratification factors are applied in this study:

- CS dose (≥ 10 mg/day or < 10 mg/day)
- SLEDAI-2K score (≥ 10 or < 10)
- Region (North America, Latin America, Japan, rest of world)

However, as CS dose and SLEDAI-2K score are not applied in Japan, the levels for the factor that is used in the analysis to represent the randomization strata is redefined as follows:

1. CS dose = ' ≥ 10 mg/day', SLEDAI-2K score = ' ≥ 10 ', Region= 'North America' ;
2. CS dose = ' ≥ 10 mg/day', SLEDAI-2K score = ' ≥ 10 ', Region= 'Latin America' ;
3. CS dose = ' ≥ 10 mg/day', SLEDAI-2K score = ' ≥ 10 ', Region= 'rest of world' ;
4. CS dose = ' ≥ 10 mg/day', SLEDAI-2K score = ' < 10 ', Region= 'North America' ;
5. CS dose = ' ≥ 10 mg/day', SLEDAI-2K score = ' < 10 ', Region= 'Latin America' ;
6. CS dose = ' ≥ 10 mg/day', SLEDAI-2K score = ' < 10 ', Region= 'rest of world' ;
7. CS dose = ' < 10 mg/day', SLEDAI-2K score = ' ≥ 10 ', Region= 'North America' ;
8. CS dose = ' < 10 mg/day', SLEDAI-2K score = ' ≥ 10 ', Region= 'Latin America' ;
9. CS dose = ' < 10 mg/day', SLEDAI-2K score = ' ≥ 10 ', Region= 'rest of world' ;
10. CS dose = ' < 10 mg/day', SLEDAI-2K score = ' < 10 ', Region='North America';
11. CS dose = ' < 10 mg/day', SLEDAI-2K score = ' < 10 ', Region='Latin America';
12. CS dose = ' < 10 mg/day', SLEDAI-2K score = ' < 10 ', Region='rest of world';
13. CS dose = Not Applicable, SLEDAI-2K score = Not Applicable, Region='Japan';

The above redefined stratification factor collected from IVRS system will be included in statistical analysis models or be used to examine treatment effect. For subgroup analysis, the value of the above redefined stratification factor collected on the eCRF will be used.

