11.7.1 Primary Endpoint

The primary efficacy endpoint is the proportion of subjects who have a SRI(4) response at Week 32 as per non-responder imputation. All subjects in the randomized population will be categorized as a responder or non-responder.

Definition of Endpoint

A responder is defined as meeting all of the following criteria. If one criterion is not met, the subject will be considered a non-responder.

- Reduction from baseline of ≥ 4 points in the SLEDAI-2K

The total SLEDAI-2K score is the sum of the scores for all items. The total score will be taken from the eCRF. A reduction in at least 4 points is achieved if SLEDAI-2K at Week 32 – SLEDAI-2K at baseline ≤ -4 .

- No new BILAG A (severe disease activity) and not more than 1 new BILAG B (moderate disease activity) organ domain grade

An A grade is new if the baseline grade for the same organ system was B, C, D or E. A B grade is new if the baseline grade for the same organ system was C, D, or E.

This criterion is met if both of the following conditions are met:

- All organ domains with an A grade at Week 32 were graded A at baseline
- The number of organ domains with a B grade at Week 32 that were graded C, D, or E at baseline is ≤ 1

- No worsening from baseline in the Physician's Global Assessment of Disease Activity scale by at least 0.3 points
 - Physician's Global Assessment of Disease Activity at Week 32 – Baseline Physician's Global Assessment of Disease Activity < 0.3

Non-Responder Imputation (NRI) Method

Subjects will be considered non-responders at a given time point per imputation (i.e. regardless of observed SRI-response as defined above) if any of the following apply:

- Subject takes any of the following prohibited medications:
 - Corticosteroid dosages above 7.5mg/day prednisone or equivalent after week 20 (Week 20+1 day)
 - Use of IM or IV CS within 8 weeks before the W32 assessment timepoint
 - Use of IA or intrabursal CS within 8 weeks before the W32 assessment timepoint

Sponsor: Bristol-Myers Squibb
Protocol no: IM011021

- Use of modified-release oral CS formulations within 8 weeks before the W32 assessment timepoint
- Addition (compared to baseline) of topical CS within 2 weeks before the W32 assessment timepoint
 - Ocular CS are allowed for non-SLE indications
 - Inhaled CS are allowed
- CS bursts/rescue above the protocol-defined maximum dosage (40 mg/day prednisone equivalent)
- More than 1 CS burst or any CS burst for treatment of SLE after week 8

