 - Oral steroid burst for non-SLE indication is permitted up to week 24 or between week 32 and week 40
- Initiation of or increases in oral NSAIDs (compared to baseline) occurring within the 7 days before the W32 assessment timepoint
- Initiation of or increase in immunosuppressant dosage/regimen and/or antimalarial dosage/regimen (compared to baseline)
 - Dose decrease or discontinuation is permitted
 - Discontinuation with subsequent restart at the same or lower dose is permitted
 - Immunosuppressants are defined as (combinations of these are not permitted): Azathioprine, 6-MP, methotrexate, leflunomide, MMF
 - Antimalarials are defined as: chloroquine, hydroxychloroquine, or quinacrine
- Subjects takes any medications included in protocol Appendix 7 between first dose date and efficacy assessment visit
- Permanent treatment discontinuation of IP before the considered time point
- Missing value for the endpoint at the considered time point
- Subjects who are lost to follow-up or discontinue the study early are considered non-responders for all time points at and after loss to follow up or study discontinuation

Primary Analysis

The primary analysis will be conducted on the randomized population.

The analysis of NRI-imputed SRI(4) response at Week 32 will be conducted using logistic regression modeling, with treatment group (four levels) and redefined stratification factor (see [section 6.5](#), thirteen levels) as fixed factors. The odds ratios of response will be estimated and tested between the BMS-986165 treatment groups and the placebo group [REDACTED]. In case the logistic regression model fit is not stable the region stratification factor may be removed from the model (resulting in 5 stratification factors: non-Japan subjects with baseline CS dose ≥ 10 mg/day and SLEDAI-2K score ≥ 10 , non-Japan subjects with baseline CS dose < 10 mg/day and SLEDAI-2K score ≥ 10 , non-Japan subjects with CS dose ≥ 10 mg/day and SLEDAI-2K score < 10 , non-Japan subjects with CS dose < 10 mg/day and SLEDAI-2K score < 10 and Japan subjects). Estimated odds ratios of response with corresponding 2-sided 95% confidence interval (CI) and p-value will be reported.

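### The primary SRI(4) model adjusts for baseline SLEDAI-2K only through a cut at 10, and not at all in Japan

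*SAP*

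**What the plan says.** SAP 11.7.1 (Primary Analysis) models NRI-imputed SRI(4) response at Week 32 by logistic regression "with treatment group (four levels) and redefined stratification factor". Part of the paragraph is blacked out after the mention of the placebo group, but the list of fixed factors before it reads as complete.

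SAP 6.5 builds the 13-level factor from corticosteroid dose (cut at 10 mg/day), SLEDAI-2K (cut at 10) and region. It gives Japan a single level: "CS dose = Not Applicable, SLEDAI-2K score = Not Applicable, Region='Japan". The stated reason is a design one: "However, as CS dose and SLEDAI-2K score are not applied in Japan".

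The values are the randomization values: "The above redefined stratification factor collected from IVRS system will be included in statistical analysis models". SAP 5.2 says randomization used the "screening SLE Disease Activity Index 2000 (SLEDAI-2K) score", so the term in the model is a screening category and not the Day 1 score.

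Protocol 9.3.1.3 matches this: the primary endpoint "will be analyzed using logistic regression with covariate for the randomization stratum". If the fit is unstable, SAP 11.7.1 drops region and keeps five levels, with the same cut and the same single Japan level.

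The first SRI(4) criterion in SAP 11.7.1 is "Reduction from baseline of ≥ 4 points in the SLEDAI-2K". SAP 7.1 measures baseline as the last value before dosing on Day 1.

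**The concern.** The starting score enters the endpoint directly, and the model holds little information about it. Subjects scoring 6 and 9 share a category, as do subjects scoring 10 and 20. In Japan all scores are pooled.

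Steroid dose has the same problem. Under the NRI rules in SAP 11.7.1, a dose above 7.5 mg/day after Week 20 makes a subject a non-responder, while Protocol 5.1 allows up to 30 mg/day at screening. A subject entering on 10 mg is 10 − 7.5 = 2.5 mg above that threshold, and one on 30 mg is 30 − 7.5 = 22.5 mg above it, yet both sit in the same category.

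If these values predict response within categories, the trial gives up some precision on its primary comparison. A chance imbalance between arms within a stratum, or within Japan, is then not adjusted for.

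**Working it through.** **Are the data available, and is the score used elsewhere?**
- SLEDAI-2K is scheduled on Day 1 for everyone (Protocol Table 2), and its total is on the eCRF (SAP 6.1). Baseline steroid dose has its own eCRF form (SAP 7.1). The Japan entry reflects how randomization was stratified, not missing data.
- No visible SRI(4) analysis uses the continuous score. The two sensitivity analyses and the COVID-19 analysis change only the imputation. The tipping-point analysis is an unstratified chi-square. The subgroups (SAP 11.7.4) reuse the cut at 10. The protocol's CMH analysis uses the same stratum.
- The joint-count MMRM in SAP 11.7.2.5 does carry a continuous baseline covariate alongside the stratum.

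**The plan's own power figure.** SAP 5.1 states at least 84% power for a 20-point difference with 90 per arm. The placebo rate and exact comparison are not visible, so this cannot be reproduced uniquely. Take the two BID arms pooled (180) against placebo (90), with two-sided alpha 0.04. The 0.04 comes from the protocol's Summary of Changes, and two-sided is assumed. Power = Φ[(d − z·s0)/s1]. At 40% against 60%:
- pooled rate (36 + 108)/270 = 0.533
- s0 = √[0.533 × 0.467 × (1/90 + 1/180)] = 0.0644
- s1 = √[0.24/90 + 0.24/180] = 0.0632
- power = Φ[(0.2 − 2.054 × 0.0644)/0.0632] = 85.8%

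Over placebo rates of 20% to 50% the range is 85.8% to 91.1%, consistent with the statement. The present point does not depend on it.

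**Effect of adding the continuous score.** The documents give no score distribution, prognostic strength, placebo rate or Japan share, so all are assumed:
- 360 subjects, 90 per arm.
- Baseline score 6 + 2 × Poisson(2.2), mean 6 + 4.4 = 10.4. The screening score differs by 2 points in a third of subjects.
- 8% in Japan; 45% on at least 10 mg/day.
- logit P(response) = a + slope × (score − 10.4) + treatment effect, with 35% response on placebo and 55% on active at the mean score, so log OR = ln(0.55/0.45) − ln(0.35/0.65) = 0.20 + 0.62 = 0.82.
- Wald test of one active arm against placebo at two-sided 0.04; 2,000 trials per slope.

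| OR per 4 points | Power, stratum only | Power, plus continuous score | Difference | Type I error, stratum only / plus score |
|---|---|---|---|---|
| 1.00 | 73.7% | 73.6% | −0.1 | 3.8% / 3.8% |
| 1.22 | 72.6% | 72.6% | 0 | 3.7% / 3.7% |
| 1.49 | 71.5% | 72.3% | +0.8 | 3.7% / 3.8% |
| 1.82 | 71.2% | 72.5% | +1.3 | 4.1% / 3.8% |
| 2.23 | 68.6% | 70.8% | +2.2 | 4.2% / 4.0% |

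The standard error of one power figure is about √(0.72 × 0.28/2000) = 1.0 point. The differences are steadier, because both models are fitted to the same trials.

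With 3,000 trials and Japan at 5% or 15%, the gains were +0.9 and +0.4 points (OR 1.49), +1.9 and +2.1 (OR 2.23), and +2.9 and +4.2 (OR 3.3).

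**On the effective-sample-size scale.** In 1,500 trials per slope with log OR 0.85, (ratio of mean z with and without the score)² − 1 was 0.6%, 1.2%, 2.3% and 3.8% for odds ratios from 1.3 to 2.7 per 5 points. Per 4 points that range is 1.3^0.8 = 1.23 to 2.7^0.8 = 2.21, so it covers much the same slopes as the table. On 360 subjects it is worth about 360 × 0.006 = 2 to 360 × 0.038 = 14 subjects.

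**The case against.** The strongest reply is that nothing here is wrong. The protocol names a model with the randomization stratum, and the SAP implements it. The single Japan level is a documented consequence of the design. Randomization makes chance imbalance a matter of variance that the standard error already allows for, not of bias. All of that stands.

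The gain is also small and assumed. In another 1,500 trials per setting with 10% in Japan, power without and with the score was 78.1% and 78.0% (OR 1.0 per 5 points), 75.7% and 75.4% (OR 1.3), and 72.7% and 72.8% (OR 1.8), which is within noise. This limits the size claimed but does not contradict it.

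SRI(4) also needs the BILAG and PGA criteria, and NRI overrides the observed response. Every subject enters with at least 6 points, so a 4-point fall is possible for all. These points stand too: SLEDAI-2K change is a necessary component, not the whole definition, and the documents do not show a gradient within categories.

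The conditional odds ratio would shift. In the OR 1.8 run the mean log OR moved from 0.870 to 0.887 and its SE from 0.321 to 0.325. That is a small change to an estimate already conditional on 13 strata. The ratio to the SE still rises slightly, from 0.870/0.321 = 2.71 to 0.887/0.325 = 2.73.

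The steroid-dose term is supported by reasoning more than by figures. When dose was given no prognostic effect, adding it changed power by at most 0.2 points; no figure is offered here for the gain if it is prognostic.

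**Conclusion.** The concern holds as a minor improvement. The primary model uses baseline SLEDAI-2K only as a screening category, and uses neither SLEDAI-2K nor steroid dose in Japan, although both are recorded for everyone. Type I error is unaffected.

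The likely gain is 0.6% to 3.8% in effective sample size for odds ratios of 1.3 to 2.7 per 5 points. That is roughly 0 to 2 points of power, and 3 to 4 only if the score is very strongly prognostic (about 3.3 per 4 points). If the score is not prognostic, the cost is negligible. These sizes depend on the assumed slope, score distribution, response rates and Japan share, and on a linear effect on the logit scale.

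**What to change.** In SAP 11.7.1, add continuous baseline SLEDAI-2K (eCRF, as defined in SAP 7.1) and baseline prednisone-equivalent dose (0 for non-users) as covariates for all regions, alongside the stratum factor. Apply the same to SRI(4) at Week 48 under SAP 11.7.2.1. State that the continuous terms stay if the five-level fallback is used, and that the odds ratio is conditional on them. Fix this before unblinding.

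If the sponsor prefers to keep the protocol's model as primary, pre-specify the extended model as a sensitivity analysis.

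The cost is a short SAP revision and one or two model terms, with no new data. Because Protocol 9.3.1.3 names only the stratum, the SAP should record the added terms as a change from the protocol.

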The number and percentage of subjects achieving NRI-imputed SRI(4) response at Week 32 and those who do not will be reported by treatment group with the estimated response rate and asymptotic 95% confidence intervals (CIs). Differences in response rates between each active treatment group and placebo with corresponding 2-sided 95% CIs based on the continuity-corrected Newcombe method will also be provided.

Tipping Point Analysis

Tipping point analysis will further be used to assess the robustness of the primary study results. Different number of events between treatment groups will be assessed until the study conclusion is

Sponsor: Bristol-Myers Squibb
Protocol no: IM011021

changed. Each imputed value is initially imputed as a responder. The imputed values in the placebo group will remain as responders while the BMS-986165 imputed values are replaced as a non-responders one at a time, therefore changing the number of events between groups. Once all imputed values in the BMS-986165 group have been replaced with non-responders values, the data will reset to where the BMS-986165 group imputed values are all responders and one by one the imputed values in the placebo group are replaced with a non-responder until all placebo are non-responders and all BMS-986165 are responders. Furthermore, every pair of imputations between the placebo and BMS-986165 groups will be assessed similarly, creating a matrix of possible patterns.

At each iteration, the statistical analysis is assessed, and the direction of the analysis is recorded. A graph will be provided to identify at what point to which the difference in events cause a direction shift in study results. The tipping point analyses will be based on a two-sample chi-square test approach rather than a stratified CMH test approach for simplicity of the analysis.

Sensitivity analysis #1 (Treatment Policy Strategy)

The primary analysis for the primary endpoint will be repeated using a treatment policy estimand approach (Intention-To-Treat (ITT) principle). For this approach, subjects will only be imputed as non-responders if there is a missing value for the endpoint at the considered timepoint.

Sensitivity analysis #2

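### The tipping-point grid for Week 32 SRI(4) mixes missing outcomes with failures by rule, defines the tip in two ways, and uses a test other than the primary one

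*SAP*

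**What the plan says.** The primary endpoint in SAP 11.7.1 is SRI(4) response at Week 32 under non-responder imputation (NRI). The NRI rule reads: "Subjects will be considered non-responders at a given time point per imputation (i.e. regardless of observed SRI-response as defined above". Its triggers include:

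- steroid dose above the limit after Week 20, and restricted or newly added medications;
- rescue: "More than 1 CS burst or any CS burst for treatment of SLE after week 8";
- "Permanent treatment discontinuation of IP before the considered time point";
- "Missing value for the endpoint at the considered time point";
- loss to follow-up or early study discontinuation, listed separately.

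The tipping-point paragraph says "Each imputed value is initially imputed as a responder". It switches values to non-responder one at a time in each group, and then "every pair of imputations between the placebo and BMS-986165 groups will be assessed similarly, creating a matrix of possible patterns". It does not define an imputed value or limit the term to missing outcomes. It says scenarios run until the study conclusion changes. It then says that at each step "the statistical analysis is assessed, and the direction of the analysis is recorded", and that a graph will show where the direction shifts. On the test: "The tipping point analyses will be based on a two-sample chi-square test approach", chosen over a stratified CMH test for simplicity.

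The primary test is a Wald test of the odds ratio (SAP 5.4.2) from a logistic model with four treatment levels and a 13-level stratum factor (SAP 11.7.1).

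**The concern.** A subject with a late steroid burst or a prohibited drug is a non-responder by definition of the endpoint. Nothing about that outcome is unknown, and the Week 32 SRI(4) may even have been observed as non-response. Read as written, the grid sets such a subject to responder. Neither sensitivity analysis does this: #1 and #2 lift rules and use the observed value.

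The analysis matters because sensitivity analyses #1 and #2 both keep a missing value as non-response, and the COVID-19 analysis alters only COVID-related gaps. The tipping-point grid is therefore the only general check on the assumption that missing means non-response. If most of the grid consists of failures by rule, a reader cannot tell whether a tip comes from missing data. Two competent programmers could also report different tipping points from the same data.

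**Working it through.** **Inputs.** About 90 subjects per arm and a 20-point design difference (SAP 5.1). The tipping-point paragraph gives no figure to reproduce, and the point does not depend on the stated power. The placebo response rate and the numbers missing or meeting an NRI trigger are not visible. I assume 54/90 active and 36/90 placebo NRI responders, and vary the number of imputed values per arm.

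**Formula.** For a and b responders of n per arm, p̄ = (a + b)/(2n) and z = [(a − b)/n] / √[2p̄(1 − p̄)/n]. This is the uncorrected two-sample chi-square; p-values are two-sided.

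**Step 1: placebo flips, active values left as non-responders.**

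| Placebo flips | Responders | Difference / SE | z | p |
|---|---|---|---|---|
| 0 | 54 vs 36 | 0.2000 / 0.0745 | 2.68 | 0.0073 |
| 4 | 54 vs 40 | 0.1556 / 0.0745 | 2.09 | 0.037 |
| 5 | 54 vs 41 | 0.1444 / 0.0744 | 1.94 | 0.052 |

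Significance is lost at flip 5, at either 0.05 or 0.04. Because 54 − 36 = 18, flip 18 gives a tie and flip 19 reverses the direction. The two criteria in the text thus give tipping points of 5 and 19.

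**Step 2: the whole grid.** With K imputed values per arm there are (K + 1)² cells. The table counts cells favouring active at two-sided 0.05.

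| K per arm | Significant cells | Worst p (all K placebo flips, no active flips) |
|---|---|---|
| 3 | 16 of 16 | 0.025 |
| 5 | 35 of 36 | 0.052 |
| 9 | 85 of 100 | 0.18 |
| 20 | 316 of 441 (72%) | 0.76, direction reversed (54 vs 56) |

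At K = 20, 441 − 316 = 125 cells lose significance. Direction reverses only where placebo flips exceed active flips by at least 19, which is 3 cells: (active, placebo) = (0, 19), (0, 20) and (1, 20).

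Other assumed rates behave alike. With 50 versus 32 responders, 16 of 16, 35 of 36, 85 of 100 and 312 of 441 cells are significant, and 5 placebo flips again remove significance.

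**Step 3: where the missing-only scenarios sit.** The chi-square depends only on counts. A grid limited to missing values is therefore a corner block of the full grid, anchored at the all-non-responder cell. Nothing in the SAP marks it.

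**Step 4: agreement with the primary test.** The all-non-responder cell holds the same data as the primary analysis but is tested differently. Simulated trials with 13 equal strata and about a 20-point effect (both assumed) gave these rates of disagreement between the chi-square and the stratified Wald test:

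| Between-stratum SD (log-odds) | At 0.05 (400 trials) | At 0.04 (2,000 trials) |
|---|---|---|
| 0 | 4.5% | 4.5% |
| 0.5 | 7.3% | 6.9% |
| 1.0 | 13.3% | 13.4% |

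**The case against.** A reader might infer that the analysis does not probe missing data at all. The documents do not support that. A missing value is an NRI trigger, so missing values are flipped and every pair is assessed. Someone who knows the number missing per arm can find the block inside the matrix. What stands is that the block is neither defined nor marked.

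Nor should the grid's first cell be expected to match the primary result. It has every imputed value as a responder. The cell to compare is the one with all of them as non-responders.

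The contrast between grids depends on assumed counts. With 3 missing per arm nothing tips; with 5, one cell does. A continuity correction, which the paragraph does not mention, would move the tip to flip 4 (p = 0.052). This shows the arithmetic is illustrative, but it does not answer the definitional point.

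The SAP discloses the unstratified test as a simplification, which is acceptable in a supportive analysis if agreement with the primary result is checked. The wording on direction may be loose drafting, since the changed conclusion is mentioned too, but both statements are there and they differ.

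Sensitivity analyses #1 and #2 do address the medication rules. That is a reason to keep those subjects out of this grid.

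The argument is weaker for subjects who stop treatment. SAP 7.2 windows efficacy data only up to last dose, so someone who stops before the Week 32 window (study days 212 to 239) has no usable value and is in effect missing. Limiting flips to subjects with no other NRI trigger would go too far: it would drop those stoppers and subjects lost to follow-up, and could understate fragility.

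**Conclusion.** The concern holds in a limited form. As written, the grid combines unknown outcomes with failures by rule, states two criteria for a tip, and uses a test that need not reproduce the primary conclusion. The likely error is to make the primary result look more fragile than missing data would. The primary estimate, test and error control are untouched.

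The size cannot be fixed from the documents. In the assumed example the tipping point is 5 or 19 placebo flips depending on the criterion. The share of significant cells falls from 16 of 16 with 3 imputed values per arm to 316 of 441 with 20. The test disagreement of about 4.5% to 13.4% depends on assumed equal strata and stratum effects. The alpha of 0.04 for the BID branch (0.01 for QD) comes from the protocol's summary of changes. The current testing strategy is not visible, so sidedness and the split between the two BID arms are unknown.

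**What to change.** Amend the tipping-point paragraph of SAP 11.7.1 as follows:

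1. Keep subjects with a medication or rescue trigger as non-responders in every cell.
2. Flip only subjects with no usable Week 32 SRI(4), including those lost to follow-up or withdrawn from the study.
3. Show subjects who stopped study treatment as a separately marked block. Reconcile the last-dose windowing in SAP 7.2 with sensitivity analysis #1, which is meant to follow a treatment-policy approach.
4. Define the tip as loss of significance at the alpha used for that active arm versus placebo, and name the arm for each grid. Direction can be shown as well, labelled as such.
5. Use the primary logistic model, or its 5-level fallback, in each cell. Results then depend on which subjects are flipped, so average over that choice. At the least, confirm with that model that the all-non-responder cell reproduces the primary conclusion.

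The cost is SAP wording and some computing time. Trial conduct and data collection do not change.
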